# STUDY PROTOCOL

# Outcomes of peptic ulcer bleeding in routine clinical practice

## Introduction

Acute upper non-variceal gastrointestinal bleeding is a very common cause of hospitalization worldwide, with an incidence that has been placed between 50 - 150 per 100,000 adults per year. Both gastric and duodenal ulcers are the most common cause of non-variceal upper-gastrointestinal bleeding. The mortality of peptic ulcer bleeding (PUB) has been reported to be between 5-14 % and remained stable despite the considerable advances observed in endoscopic and pharmacological treatments. The reasons for this are unclear, but a progressive aging population and the subsequent increase of co-morbidities may explain part of this apparent paradox.

Randomized clinical trials are the gold standard for determining the efficacy of therapies. Clinical guidelines and expert recommendations in the management of PUB are mostly based on these RCTs. The most recent RCT has reported that endoscopic therapy plus IV high-dose esomeprazole in high-risk patients for re-bleeding based on endoscopic findings, was associated with 5.9% of recurrent bleeding within 72 hours, 6.4% of endoscopic retreatment, 2.7% in need of surgery to control the bleeding event and a low mortality of 0.8% (Sung et al 2009). However, in agreement with regulatory agencies it is unclear or unknown how these recommendations are applied and the actual outcomes of PUB in clinical practice.

## **Objectives:**

1. To assess outcomes in clinical practice in patients hospitalized due to PUB and treated with high-dose IV infusion PPI plus standard endoscopy therapy in patients with endoscopic high risk stigmata (spurting bleeding, visible vessel, oozing bleeding, red clot attached to the ulcer niche): overall and among individual PPI (esomeprazole and pantoprazole).

2. To assess outcomes in clinical practice in patients hospitalized due to PUB and treated with IV infusion PPI plus endoscopy therapy, if needed: overall and among individual PPI (esomeprazole and pantoprazole).

## **Methods**

## Study design and patients

This will be a multicenter retrospective observational study carried out in Spain. In order to prevent selection bias in pharmacotherapy, participating centers will be selected if they use routinely a single IV PPI (esomeprazole or pantoprazole) in the management of PUB events.

The eligible patients will be all consecutive patients hospitalized due to PUB and selected according to codes from ICD9 which identify gastric and duodenal ulcer bleeding (Table I). Patients will be included retrospectively from

till completion of the desired sample size, which was estimated to be between ).

Eligible patients will be those complying with the following characteristics: a) age (≥18 years) admitted to the hospital with an overt upper GI bleed due to peptic ulcer and manifested as hematemesis/coffee ground vomiting, melena, hematochezia and other clinical or laboratory evidence of acute blood loss from the upper GI tract; b) evidence that an upper GI endoscopy was performed; c) IV PPI (esomeprazole or pantoprazole) had to be used after the endoscopy procedure d) complete medical records available for the study-related

3

hospitalization. Exclusion criteria are: patients with terminal malignant disease (life expectancy less than 6 months), required treatment with ASA or NSAIDs for the next 3 days during hospital after endoscopic therapy, or suffering from haematological disease associated with severe dyscrasia (e.g haemophilia)

Information regarding patient's characteristics, drug use before the PUB event, co-morbidities, symptoms, signs and severity of the event at hospital admission, endoscopic findings, endoscopic therapy, pharmacological therapy including type of drug, dose, route an type of administration, and outcomes will be collected from each patient's hospital medical records.

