## Data management and quality assurance

A unique *Case Report Form* will be provided to all participating centers. There will be no possibility of adapting, changing or adding any different data to those gathered in the CRF. Although investigators from this hospital network in Spain have participated in a substantial number of studies collecting data either prospectively or retrospectively from charts, and in order to comply with data quality requirements, investigators will be trained in the use of CRF in advance (Lanas et al. Am J Gastroenterol 2009, ENERGIB study). Based on a sample of patients, investigators will also have to confirm in advance that medical records are compatible with the required data collection of the CRF. Furthermore, each CRF will be monitored for data consistency and accuracy. A sample of data recorded in the CRF from patients from each study centre will be evaluated by the study coordinator.

A specific computer program will be developed for data entry of each individual item collected in the CRF. Trained and experienced staff in managing databases will carry out the data entry. The database will be designed to minimize data entry errors,

In order to guarantee the confidentiality of the patients' data, only the hospital personnel will have access to the medical records. The study physicians will review the clinical charts and will fill in the data collection sheet with the relevant information. The clinical identification number will be recorded in the database

for data management purposes, but it will not be exported to the data analysis files to guarantee the patients' confidentiality. During the data entry process, a random fictitious identification number is created for each case, which will be the only identification available in the analysis files.

When the data collection and entry are completed, the information in the database will be exported to statistical analysis software, which will only contain the patients' fictitious identification created in the data entry process and not the clinical identification number, therefore preserving the patients' confidentiality during the data analysis process.

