## **Statistics**

Sample size. Based on a recent international observational study on PUBs (Energib) the estimated re-bleeding rate was over 8% and the overall mortality rate of PUBs around 5%. It is assumed that these proportions will be increased between 1.5- and 2-fold in patients with high-risk stigmata that represent approximately between a third and a fourth of our total PUB study population. Assuming a 1.25% error for the lowest proportion and a 2.5% for the largest one, with an alpha value of 0.05, we have estimated a sample size of 1100 patients per group of PPI treatment for the overall PUB cohort to be studied and 400 - 500 per group (esomeprazole and pantoprazole) for those with high-risk stigmata.

Due to the study design, variables will be presented by descriptive statistics. Categorical data will be reported as frequencies and proportions. Continuous data will be reported as means and standard deviations. Where appropriate, alternate descriptive statistics such as quartile ranges, and medians with ranges for categorical and continuous data respectively will be reported. Analyses will be performed, overall, in patients with high-risk stigmata and according to individual PPI.

Although the objective of the study is to provide rates of outcomes of the different cohorts of PUB patients studied, potential differences in outcomes across different risk strata (age, co-morbidities, endoscopic findings, etc..) will be analysed with the Chi-square test for categorical variables and with t-test for continuous data. A variance analysis will be performed for multiple comparisons. Multivariable logistic regression models will also be fitted to define determinants of outcomes.

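### The drug groups are formed by centre, but the stated precision per PPI assumes independent patients, so the 1.25% and 2.5% margins are optimistic and PPI cannot be separated from centre

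*Protocol*

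**What the plan says.** The Study design and patients section describes the design: "This will be a multicenter retrospective observational study carried out in Spain". It then gives the selection rule, "participating centers will be selected if they use routinely a single IV PPI (esomeprazole or pantoprazole", and offers it as a safeguard against bias in the choice of drug. The Objectives section asks for outcomes "overall and among individual PPI (esomeprazole and pantoprazole" in both the high-risk and the general cohort.

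The Statistics section starts from the rates of an earlier observational study: "the estimated re-bleeding rate was over 8% and the overall mortality rate of PUBs around 5" percent. It assumes these are 1.5 to 2 times higher in patients with high-risk stigmata. With an error of 1.25% for the lowest proportion, 2.5% for the largest and alpha 0.05, it arrives at 1100 patients per PPI group overall and 400 to 500 per PPI group in the high-risk cohort.

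The same section calls the presentation descriptive. Differences across risk strata such as age, co-morbidities and endoscopic findings "will be analysed with the Chi-square test for categorical variables and with t-test for continuous data". It adds: "Multivariable logistic regression models will also be fitted to define determinants of outcomes". It mentions no number of centres, no ICC, no design effect and no role for centre in any analysis.

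**The concern.** If each hospital uses one drug, each per-PPI rate is an average over the hospitals that use that drug. Patients in one hospital share case mix, endoscopic skill and the threshold for surgery, so their outcomes are likely to be correlated. A margin of error computed as if all 1100 patients were independent then claims more precision than the design gives.

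Selecting single-PPI centres also moves the confounding without removing it. Choice of drug for the individual patient is limited, but whatever differs between the two sets of hospitals now travels with the drug. A reader who sees the two rates side by side, or a PPI term in a model of determinants, could attribute to the drug what belongs to the hospitals. An ordinary logistic model would also give too small a standard error for any factor that is constant within centre, PPI included.

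**Working it through.** **Inputs from the protocol (Statistics).** Mortality about 5%; high-risk multiplier 1.5 to 2, so high-risk mortality 7.5% to 10%; margins 1.25 and 2.5 points; alpha 0.05 (taken as two-sided, z = 1.96); 1100 per PPI overall, 400 to 500 per PPI high-risk.

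**Inputs assumed, because the protocol gives none.** ICC 0.01 to 0.05; 10 or 25 centres per PPI, of equal size.

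**Step 1: reproduce the plan's figure.** n = z² p(1−p)/d².

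- p = 5%, d = 1.25 points: 1.96² × 0.05 × 0.95 / 0.0125² = 1168. The protocol states 1100, so this is close but not exact (a rate of 4.7% would give 1102).
- p = 7.5%, d = 2.5 points: 427, inside the stated 400 to 500.

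The stated sizes are therefore of the kind that the independent-patient formula gives. The 1100 is slightly below that formula's answer, so it holds no allowance for clustering.

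**Step 2: half-width under independence.** 1.96 × √(0.05 × 0.95/1100) = 1.29 points. The first 0.04 above 1.25 is thus not due to clustering.

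**Step 3: half-width with clustering.** Design effect DE = 1 + (m−1) × ICC, with m patients per centre; effective n = 1100/DE; half-width = 1.29 × √DE.

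| Centres per PPI | m | ICC | DE | Effective n | Half-width (points) |
|---|---|---|---|---|---|
| 25 | 44 | 0.01 | 1.43 | 769 | 1.54 |
| 25 | 44 | 0.02 | 1.86 | 591 | 1.76 |
| 25 | 44 | 0.05 | 3.15 | 349 | 2.29 |
| 10 | 110 | 0.01 | 2.09 | 526 | 1.86 |
| 10 | 110 | 0.02 | 3.18 | 346 | 2.30 |
| 10 | 110 | 0.05 | 6.45 | 171 | 3.27 |

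**Step 4: high-risk cohort.** With 400 per PPI and p = 7.5%, independence gives 2.58 points. With 10 centres per PPI (m = 40), ICC 0.01 to 0.05 gives DE 1.39 to 2.95 and a half-width of 3.04 to 4.43 points, against 2.5 stated.

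**Step 5: PPI and centre.** With one routine drug per hospital, there is almost no contrast between the drugs within a hospital. A model with fixed centre effects could therefore hardly estimate a PPI effect, and a model without centre would attribute hospital differences to the drug.

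**The case against.** The strongest reply is that the study is descriptive. Its declared aim is to report rates, raw proportions answer that aim, and much of the modelling detail may properly sit in a statistical analysis plan that is not shown. This stands as far as it goes: silence on the covariates and on the variance method is not an error in a protocol. It does not cover the margin of error, which the protocol itself fixes per PPI group and which a later analysis plan cannot improve.

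A reader might infer four stronger things that the protocol does not support.

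- *That a test of esomeprazole against pantoprazole is planned, with an inflated type I error.* None is stated. The chi-square and t-tests are assigned to risk strata. PPI is not named there, although the list of strata is open-ended. The strata that are named vary within hospitals, so the design effect above is not the right inflation for those tests.
- *That reported intervals will be too narrow.* No intervals are specified for the results. The criticism applies to the planning margins and to any naive interval computed later.
- *That centre is removed from the analysis file.* The Data management section says of the fictitious patient number "which will be the only identification available in the analysis files". In context this concerns patient identity and confidentiality. Table 2 lists no centre code, but that is silence. The same section has data sampled from each study centre, so centre is known.
- *That differences between the PPIs are centre differences.* The supportable statement is that the two cannot be separated. The selection rule also says routine use, which allows individual exceptions, and the bias it claims to prevent can be read as patient-level choice of drug only.

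The size is also open. With an ICC of 0.002 and 44 patients per centre, DE is 1.09 and the half-width only 1.34 points.

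**Conclusion.** The point holds as a moderate one, about planning and interpretation. The per-PPI margins of 1.25% and 2.5% assume independent patients in a design where the drug follows the hospital. They are optimistic for any positive ICC. How optimistic cannot be settled from the protocol: for 5% mortality the range is about 1.5 to 2.3 points with 25 centres per PPI and 1.9 to 3.3 with 10, if the ICC lies between 0.01 and 0.05 and centres are of equal size. Independently of those assumptions, the design cannot distinguish a PPI effect from a centre effect, and choosing single-PPI centres does not remove confounding between centres.

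**What to change.** 1. In the Statistics section, state the number of centres per PPI and an assumed ICC, and restate the per-PPI margins with the design effect. Enrolment need not rise; the claim of precision changes.
2. Say explicitly that a coded centre identifier is kept in the analysis file next to the fictitious patient number. This does not affect patient confidentiality as described.
3. Compute any per-PPI confidence intervals, and fit the logistic models, with centre as the cluster: robust variance with a small-sample correction, GEE, or a random centre intercept. Do not use fixed centre effects, which are nearly collinear with PPI.
4. Label the per-PPI results as descriptive and not comparative, and state that single-PPI centres limit drug choice for the patient but leave differences between centres.

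The cost is one coded variable, slightly different models, wider intervals and a less favourable stated precision.

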## Data, measurements and endpoint definitions

We will collect data recorded in charts in a pre-specified Case Report Form. Main data from each patient will include demographics, diagnostic procedures and both non-pharmacological and pharmacological treatments received by patients as summarized in Table II.

Therapeutic endoscopy will be considered any endoscopic action (injection, clips, thermo-coagulation, etc...) implemented to control the bleeding event in the presence of spurting bleeding, oozing bleeding, visible vessel, and/or clots attached to the ulcer niche. Endoscopic re-treatment will be considered when any repeated procedure occurred within 30 days from the index hospital admission due to re-bleeding from the PUB episode. High-dose IV PPI will be considered the administration of either esomeprazole or pantoprazole by infusion at the dose of 8 mg/hour. However, due to the variability of clinical practice and for the purpose of this study, the administration of equivalent doses of the PPI by injection within each 24-hour period will also be considered. The dose, route and type of administration will be recorded for each patient.

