## Definitions for outcome endpoints:

- a) Bleeding continuation up to 3 days after initial treatment:
  - 1. Spurting from an artery at the initial endoscopic examination which did not respond to endoscopic therapy.
  - 2. Persistence of bleeding following initial endoscopy determined by the presence of a red bloody naso-gastric aspirate, and/or shock with a pulse greater than 100 beats/min, a systolic blood pressure of under 100 mmHg, or both, and/or the need for substantial replacement of blood and fluid volume (transfusion of more than 3 units of blood within 4 h.) following endoscopic therapy and aimed to maintain the hemodynamic stability.
- b) Re-bleeding at 3, 7 and 30 days is defined, following initial successful endoscopic treatment, including resuscitation if indicated, as recurrent vomiting of fresh blood, melena, or both with either shock or a decrease in haemoglobin concentration of at least 20 g/l This could occur during the same hospitalization and after discharge (up to 30 days from the PUB episode).
- c) Surgery at 3, 7 and 30 days: the need of surgical intervention to control the bleeding event. This could occur during the same hospitalization and after discharge (up to 30 days from the PUB episode).
- d) Mortality at 3, 7 and 30 days: Death of patients during hospitalization (inhospital mortality) or after discharge (up to 30 days from the PUB episode).

- 1. Deaths will be related to the bleeding event: death from uncontrolled bleeding, death within 72 hours of endoscopy, death during surgery for uncontrolled bleeding, death from surgical complications or endoscopic-related death.
- Deaths will be considered unrelated to the bleeding event if them were due to cardiac, cerebro-vascular, pulmonary or terminal malignant diseases or multi-organ failure causes.
- e) Other outcomes will include days of hospitalizations, need of blood units transfused (total number).

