## Management of PUB after endoscopy

PPI: route, type of PPI, dose, type of administration and time

Vasoactive drugs: drug, route, dose and type of administration

Units of blood transfused

H. pylori status, treatment

Unit managing the PUB event

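### Neither the IV PPI entry rule nor the high-dose definition requires treatment to begin before a re-bleed, so patients can be counted as treated because they re-bled

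*Protocol*

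**What the plan says.** Eligibility criterion c) (Protocol, Study design and patients) reads: "IV PPI (esomeprazole or pantoprazole) had to be used after the endoscopy procedure". It gives no start time and no ordering relative to outcomes.

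The section Data, measurements and endpoint definitions sets the exposure class: "High-dose IV PPI will be considered the administration of either esomeprazole or pantoprazole by infusion at the dose of 8 mg/hour". It then adds that "the administration of equivalent doses of the PPI by injection within each 24-hour period will also be considered". The 24-hour phrase makes injected and infused doses comparable; it does not say when treatment must start.

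Both objectives define their cohorts by treatment received. Objective 1 concerns patients "treated with high-dose IV infusion PPI plus standard endoscopy therapy in patients with endoscopic high risk stigmata", and objective 2 patients "treated with IV infusion PPI plus endoscopy therapy, if needed".

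Re-bleeding, surgery and death are counted at 3, 7 and 30 days. For re-bleeding the protocol says: "This could occur during the same hospitalization and after discharge (up to 30 days from the PUB episode"). Endoscopic re-treatment is "any repeated procedure occurred within 30 days from the index hospital admission due to re-bleeding from the PUB episode", so treatment given in response to a re-bleed is expected within follow-up.

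Table 2 (Management of PUB after endoscopy) lists "PPI: route, type of PPI, dose, type of administration and time". No rule in the protocol uses the time item.

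**The concern.** The cohorts are defined by treatment received, and the outcome itself can trigger that treatment. Take a patient with high-risk stigmata whose ulcer is treated endoscopically, who starts on a lower-dose regimen, re-bleeds during the admission and is then moved to 8 mg/hour. By the wording, this patient can be counted in the high-dose cohort with a re-bleed. The same patient without a re-bleed stays outside that cohort. Numerator events are added while their event-free counterparts are missing from the denominator.

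The Statistics section says that the purpose of the study is to report outcome rates in these cohorts, so a distortion of the rate is a distortion of the main result. A larger sample does not reduce it.

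**Working it through.** **1. Does any text close the gap?** Four places could.
- Criterion c): requires use after endoscopy, with no window and no ordering against events.
- High-dose definition: gives dose and injection equivalence, with no start time or duration.
- Choice of centres by their standard IV PPI: governs which agent is used, not when it starts or at what dose.
- Time item in Table 2: tied to no rule, and it does not say whether start or duration is meant.

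None requires treatment to precede the outcome.

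**2. The plan's own figures.** The protocol gives no figure for this bias. The nearest yardstick is its planned precision. Inputs from the Statistics section: re-bleeding 8%, mortality 5%, both multiplied by 1.5 to 2 with high-risk stigmata (re-bleeding 12-16%, mortality 7.5-10%); errors of 1.25 and 2.5 points; alpha 0.05, taken as two-sided.

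With n = 1.96² p(1-p)/d² and d = 2.5 points, p = 7.5% gives 426 and p = 8% gives 452. Both lie in the stated 400-500 per group. (For 1100, p = 5% with d = 1.25 points gives 1168. That mismatch is a separate matter and is not used here.) At a rate of 12%, the 95% half-width is 3.18 points with 400 patients and 2.85 with 500.

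**3. Formula.** Let r be the re-bleeding rate, s the share not on the qualifying regimen before any re-bleed, and q the probability that a re-bleed among them leads to that regimen. With the same r in both groups:

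observed rate = [(1-s)r + s·r·q] / [(1-s) + s·r·q]

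The document gives neither s nor q; both are assumptions.

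**4. Objective 1, r = 12%.**

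| s | q | Numerator | Denominator | Observed | Shift (points) |
|---|---|---|---|---|---|
| 10% | 0.5 | 0.108 + 0.006 | 0.900 + 0.006 | 12.6% | 0.6 |
| 10% | 1 | 0.108 + 0.012 | 0.900 + 0.012 | 13.2% | 1.2 |
| 20% | 0.5 | 0.096 + 0.012 | 0.800 + 0.012 | 13.3% | 1.3 |
| 20% | 1 | 0.096 + 0.024 | 0.800 + 0.024 | 14.6% | 2.6 |

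In patients, with 450 in total and s = 20%: 360 × 0.12 = 43.2 events among high-dose starters and 90 × 0.12 = 10.8 among the others. Half escalated gives 48.6/365.4 = 13.3%; all escalated gives 54/370.8 = 14.6%.

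Sensitivity:
- s = 5%: 12.3-12.6%.
- r = 16%, s = 10-20%, q = 0.5-1: 16.7-19.2%.
- Other starters re-bleed at half the rate (6%), q = 0.8: (0.108 + 0.0048)/0.9048 = 12.5% at s = 10%, and (0.096 + 0.0096)/0.8096 = 13.0% at s = 20%.
- At r = 12%, the shift reaches the planned 2.5 points when s is about 20% (q = 1) to 33% (q = 0.5).

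**5. Objective 2, r = 8%.** At s = 10% the formula gives 0.076/0.904 = 8.4% to 0.080/0.908 = 8.8%. For that share this overstates the effect, because it treats every re-bleed as a counted event. The endpoint definition counts re-bleeding only once a first endoscopic treatment has succeeded, so a low-risk patient who never had endoscopic therapy would not add a re-bleed on that wording.

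**The case against.** The natural reading of criterion c) is treatment straight after the index endoscopy, since it follows the criterion that an endoscopy took place. That is probably what was meant. But the wording does not say so, and even when tied to the index endoscopy it sets no limit before an outcome.

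Centres are selected because one IV PPI is their standard, so few patients may start on an oral PPI. This stands as a limit on size, mainly for objective 2. It bears less on dose, where the protocol itself acknowledges that practice varies.

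Assigning exposure by first regimen could be left to the analysis plan. This stands in part. A patient started on lower-dose IV PPI is enrolled anyway and could be reclassified later. An event-free patient never given IV PPI is not enrolled, so analysis cannot restore that part of the denominator. Removing those who entered after a re-bleed, or reclassifying them, needs the order of regimen and event. Table 2 names neither a regimen sequence nor a re-bleeding date.

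The illustrated shifts for objective 1 at 12% (0.6 to 2.6 points) lie inside the sampling half-widths of 2.85 to 3.18 points. That is correct, but a systematic shift adds to sampling error and does not shrink with more patients.

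A reader might go further and infer that all outcomes, mortality included, are inflated. The document does not support that: a late starter must survive until treatment begins, which lowers early deaths and works against any excess risk after a re-bleed. Nor does it support a bias between esomeprazole and pantoprazole in a known direction. The per-PPI rates would shift unequally only if escalation habits differed between centres, and nothing is said on that.

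**Conclusion.** The point holds as a defect in two definitions. As written, they allow cohort membership to be decided by a re-bleed in the index admission. The effect on the re-bleeding rate is upward, and probably so for surgery; for mortality it is uncertain. Objective 1 is the most exposed. For objective 2 the effect on re-bleeding is limited by the endpoint definition.

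The size is not known. The 12.6-14.6% against a planned 12% rests on assumed shares of 10-20% not on the high-dose regimen before a re-bleed, on half to all of their re-bleeders being escalated, and on equal re-bleeding rates in both groups. If few patients start on another regimen, the shift is small. A reader might conclude that the reported rates will be materially wrong; the document shows only that nothing prevents it.

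**What to change.** Define cohort entry in criterion c), high-dose status and individual PPI by the first PPI regimen after the index endoscopy. That regimen should begin within a window that the sponsor pre-sets and before any re-bleeding, repeat endoscopic treatment or surgery. Report later starts, escalations and switches separately, not as exposure. In Table 2, clarify the time item as start time and record its order relative to re-bleeding.

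This defines the analysis cohort; it is not a treatment rule. It is best settled before charts are abstracted.

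Cost: one sentence in eligibility, one in the high-dose definition and one clarified CRF item that includes the ordering. A few rescue-treated patients drop out or change class.

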## Main outcomes:

- a) Bleeding continuation up to 3 days
- b) Re-bleeding at 3, 7 and 30 days
- c) Surgery at 3, 7 and 30 days
- d) Mortality at 3, 7 and 30 days

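### The ASA/NSAID exclusion is worded on the 3 days after endoscopic therapy, so entry can depend on the 3-day outcomes and the rule acts unevenly in the overall cohort

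*Protocol*

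**What the plan says.** The Methods (Study design and patients) state: "This will be a multicenter retrospective observational study carried out in Spain". The target is broad: "The eligible patients will be all consecutive patients hospitalized due to PUB". Among the exclusions are patients who "required treatment with ASA or NSAIDs for the next 3 days during hospital after endoscopic therapy". The protocol does not say at what moment the requirement is judged, or how to classify a patient who re-bleeds, is operated on or dies before the 3 days have passed.

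The Main outcomes include "Bleeding continuation up to 3 days", "Re-bleeding at 3, 7 and 30 days", surgery at the same time points and "Mortality at 3, 7 and 30 days". Under Definitions for outcome endpoints, bleeding continuation runs from initial treatment and re-bleeding from successful initial endoscopic treatment.

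The second objective covers patients "treated with IV infusion PPI plus endoscopy therapy, if needed", so it includes patients who had no endoscopic therapy.

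Table 2 lists ASA and NSAID use before admission. Its section on management after endoscopy has no such item.

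**The concern.** A criterion for entering a cohort should be settled by what is known when follow-up starts. Here the abstractor sees the whole chart, and the wording points to the days after endoscopic therapy. Take two similar patients with a cardiovascular indication. One is stable and is given ASA over those days, so he is excluded. The other re-bleeds or dies on day 1, is never given ASA, and stays in the cohort with an event. If centres apply the rule this way, inclusion depends partly on early outcome, and no analysis of the retained patients can undo that.

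There is a second fault. Because the rule is tied to endoscopic therapy, a patient needing ASA is removed from the overall cohort if treated endoscopically and kept if not. That affects the overall rates and the planned comparison across endoscopic findings.

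The study exists to report outcome rates, so selection on outcome bears directly on its main result.

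**Working it through.** **Yardstick.** The Statistics section plans for errors of 1.25 and 2.5 percentage points. With n = 1.96² p(1−p)/d², p = 5% and d = 1.25%, n = 1168 against the stated 1100 per PPI group. At 1100 the half-width is 1.29 points for a 5% rate and 1.60 points for 8%. The stated size is therefore not reproduced exactly, but it is close, and nothing below depends on it.

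**Inputs.** From the Statistics section: re-bleeding 8% (88 of 1100), mortality 5%, rates 1.5 to 2 times higher with high-risk stigmata (12–16% for re-bleeding), and such patients a third to a fourth of the cohort. Assumed, because the protocol gives no figure: the share f excluded, 2–20%; the proportion of re-bleeds that fall by day 3, half or all; and the relative risk RR of those excluded, 1–3.

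**Timing effect on re-bleeding.** Suppose a share f of patients event-free at day 3 is excluded and no patient with an early event is. With E early and L late events among N patients:

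reported rate = (E + (1−f)L) / (E + (1−f)(N−E))

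| f | Half early (E = L = 44) | All early (E = 88, L = 0) |
|---|---|---|
| 2% | 87.12/1078.88 = 8.1% | 88/1079.76 = 8.1% |
| 5% | 85.8/1047.2 = 8.2% | 88/1049.4 = 8.4% |
| 10% | 83.6/994.4 = 8.4% | 88/998.8 = 8.8% |
| 20% | 79.2/888.8 = 8.9% | 88/897.6 = 9.8% |

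Only the last cell moves the rate by more than 1.25 points (+1.8).

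**High-risk stigmata.** The same formula over the same range turns 12% into 12.1–14.6% and 16% into 16.1–19.2%. The shift passes 2.5 points only at f = 20% with all events early: 0.12/(0.12 + 0.8×0.88) = 14.6% and 0.16/(0.16 + 0.8×0.84) = 19.2%.

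**Literal reading, treated patients only.** The table applies f to the whole cohort. Suppose instead that only a third of the 1100 (366.7) are treated, with 12% re-bleeding (44 events, all early), and that 20% of the 322.7 event-free treated patients go (64.5). The overall rate then reads 88/1035.5 = 8.5%. The effect on the overall rate is smaller and falls on one stratum.

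**Timing effect on 3-day mortality.** If only patients alive through day 3 can meet the criterion, the reported rate is m/(1 − f(1−m)). For an assumed m = 2% this gives 2.04% at f = 2% and 0.02/0.804 = 2.49% at f = 20%.

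**Case-mix effect, in the other direction.** If those excluded have RR times the risk of the rest and are removed whatever their outcome, the reported rate is p/(1 − f + f·RR).
- Re-bleeding, f = 10%, RR = 2: 0.08/1.1 = 7.3%.
- Mortality of 5%: 4.90% at f = 2%, RR = 2; 0.05/1.4 = 3.57% at f = 20%, RR = 3; no change at RR = 1.

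The two effects oppose each other, and the protocol gives no figure that would settle which is larger.

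**The case against.** The strongest reply is that the text speaks of treatment being required, not received. A need for the coming 3 days can be one foreseen at endoscopy, which is a baseline criterion, and charts can show it: cardiovascular disease and prior ASA/NSAID use are collected. A patient whose ASA is resumed only on day 2 does not plainly meet a criterion that speaks of the next 3 days. This stands. Outcome-dependent entry is what one natural reading produces, not the only possible reading. But the protocol does not choose between the readings, and centres could differ.

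The reply is also right on size. At shares of 2–5% the shift in an 8% rate is at most about 0.4 points. The assumption that no early-event patient is excluded is not secure either: a patient given ASA from the start who re-bleeds on day 2 would be removed with the event, which lowers the rate.

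Three stronger readings are tempting, and the protocol does not support them.
- *The rule removes the comorbid patients.* The Introduction says of stable mortality that "a progressive aging population and the subsequent increase of co-morbidities may explain part of this apparent paradox", so the inference is natural. But comorbidity is not an exclusion; it is collected in Table 2 and analysed as a risk stratum. Only patients needing ASA or NSAIDs in a short window go, and their number and risk are not given.
- *The cohort becomes a copy of a trial population.* The protocol gives the results of the cited randomised trial but not its eligibility rules, so this cannot be checked.
- *The exclusion must be dropped.* A descriptive study may restrict its target population openly. The fault lies in when and to whom the rule applies.

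**Conclusion.** The point holds in a limited form. As worded, the exclusion lets eligibility in a retrospective study turn on the days in which the early outcomes are counted, and read literally it applies to only part of the cohort in the second objective. A reading as a need known at endoscopy is open but not stated.

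A reader might infer that the reported early rates will be too high. The protocol does not support a direction. On assumed shares of 2–20%, with no early-event patient excluded, an 8% re-bleeding rate would read about 8.1–9.8%. With a higher-risk excluded group it could read lower, for example 7.3%. The shift passes the planned precision only at the extreme of the assumed ranges. Nothing shows that the rule acts differently in the two PPI groups. The change is still worth making before abstraction, because it is cheap and the selection cannot be repaired afterwards.

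**What to change.** 1. Reword the exclusion so that it rests only on an ASA/NSAID requirement documented at or before the index endoscopy.
2. Apply it whether or not endoscopic therapy was given.
3. Add a CRF item for in-hospital ASA/NSAID use with its start date, unless the prepared form already has one; only the Table 2 list is visible here. This must be done centrally and before abstraction, since Data management and quality assurance does not let centres alter the form.
4. Report the number excluded for this reason.
5. Optionally, add a sensitivity table that includes those patients. Their outcomes would then have to be abstracted too.

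The cost is one reworded criterion, one CRF item and slightly more abstraction work. Some patients given ASA or NSAIDs after endoscopy will remain in the main cohort. No view is taken on whether ASA or NSAIDs should be given.
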